**Table 7. SAS code for tipping point analysis**

---

```
proc mi data= OUT_IMP_CONT (where=(TRT="RIC")) nimpute=1 round=
  seed= out=IMPDAT_TRT;
  by _IMPUTATION_;
  var BASE_NRS CONMED
      DELT_NRS1 DELT_NRS2 DELT_NRS3 DELT_NRS4
      DELT_NRS5 DELT_NRS6 DELT_NRS7 DELT_NRS8
      DELT_NRS9 DELT_NRS10 DELT_NRS11 DELT_NRS12;

  monotone reg (/details);

  mnar adjust (DELT_NRS /shift=&S.);
run;

data COMBINE;
  set IMPDAT_TRT IMPDAT_PBO;
run;
proc sort data=COMBINE;
  by _IMPUTATION_;
run;
```

---

## 8. Key secondary analyses

### 8.1. Estimands

There are two key secondary outcomes: the change from baseline in the NRS at Week 4 and the change from baseline in the UENS at Week 12. The estimands for the NRS at Week 4 and the UENS at Week 12 are described in Table 8 and Table 9, respectively.

**Table 8. Estimand attributes for the key secondary outcome of change from baseline in NRS at Week 4**

Estimand attribute	Description
Population	Full analysis set population, which consists of all patients who receive at least one dose of study drug and have baseline average pain intensity score and at least one post-baseline average pain intensity score.
Endpoint	Change from baseline in the weekly mean of daily average pain based on the 11-point NRS at Week 4.
Intercurrent events	All values collected after treatment discontinuation will be included in the analysis. All missing values due to treatment or study discontinuation will be imputed using reference-based imputation with missing values imputed based on the placebo data. All other intermittent missing values will be imputed under the assumption of missing at random with each missing value imputed based on the treatment group assignment. This hypothetical scenario assumes that the treatment had no further benefit in patients that discontinued study medication while accounting for the disease trajectory and trial effect.
Summary measure	Difference between ricolinostat arm and placebo arm as measured by change from baseline in average pain at Week 4.

**Table 9. Estimand attribute for the key secondary endpoint of UENS at Week 12**

Estimand attribute	Description
Population	Full analysis set population, which consists of all patients who receive at least one dose of study drug and have baseline average pain intensity score and at least one post-baseline average pain intensity score.
Endpoint	Change from baseline in weekly mean of daily average pain based on the UENS at Week 12.
Intercurrent events	All values collected after treatment discontinuation will be included in the analysis. All missing values due to treatment or study discontinuation will be imputed using reference-based imputation with missing values imputed based on the placebo data. All other intermittent missing values will be imputed under the assumption of missing at random with each missing value imputed based on the treatment group assignment. This hypothetical scenario assumes that the treatment had no further benefit in patients that discontinued study medication while accounting for the disease trajectory and trial effect.
Summary measure	Difference between ricolinostat arm and placebo arm as measured by change from baseline in average pain at Week 12.

The analyses will follow those used for the primary efficacy analyses with a MMRM and multiple imputation as described in Section 7.

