#### **10.3.4 Key Secondary Outcome Measures**

The key secondary outcome measures are the change from baseline in the mean NRS score at Week 4 and the change in non-pain neuropathic signs and symptoms after 12 weeks as assessed by change in the UENS.

For the first outcome of the change from baseline in the mean NRS score at Week 4, the analysis approach will be identical to that for the primary outcome, with the outcome consisting of the Week 1 through Week 4 average NRS measures. The result will be obtained from the MMRM model that is fit for the primary analysis. The estimated difference in the change from baseline between the treated and placebo groups at Week 4 will be computed as part of the primary analysis. This outcome will only be formally tested if the p-value associated with the primary

outcome is less than 0.05. If the p-value associated with the primary outcome is not statistically significant, a nominal p-value for the key secondary outcome will be presented.

The second endpoint of the change in the UENS from baseline to Week 12 will be formally tested only if the p-value associated with the key secondary outcome of change from baseline in mean NRS score at Week 4 is statistically significant. To assess this outcome, an ANCOVA model will be fit including the change from baseline in UENS at Week 12 as the outcome and baseline UENS score, treatment group, and use of concomitant medication for painful DPN (yes vs. no) as covariates.

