### **7.2. Identification of the primary model**

The primary endpoint is change from baseline in mean average pain intensity over the 12 weeks of treatment as measured by the weekly average NRS in the FAS population. The primary endpoint will be analyzed using a MMRM analysis. The MMRM will be fit with the weekly mean change from baseline in the NRS score at Weeks 1, 2, 4, 8 and 12 as the outcome. The following covariates will be included in the model: baseline NRS score, visit, treatment group, concomitant medication for painful DPN (yes vs. no), treatment group by visit interaction term, and baseline NRS score by visit interaction. A restricted maximum likelihood will be used as the method of estimation with the degrees of freedom approximated using the

Kenward Rogers approach (see Table 4 for an example of the MMRM code to be used for the primary model). The model will be fit with an unstructured covariance matrix. If the MMRM with an unstructured covariance matrix does not converge, the following covariance structures will be substituted in the order listed below. Each subsequent covariance structure will be used only if each previous covariance structure fails to converge. The covariance structure for the final model will be the first structure in the sequence that produces a stable model that converges.

1. Toeplitz covariance structure (assuming measurements taken closer together in time are more highly correlated than those taken farther apart).
2. First order auto-regressive (AR[1]) covariance structure (assuming measurements taken closer together in time are more highly correlated than those taken farther apart, but more constrained than the Toeplitz structure).
3. Compound symmetry covariance structure (assuming equal correlation for measurements from a patient, regardless of how far apart in time when they were taken).

Once the primary model is established, this model will be used for all analyses.

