## 9. Secondary analyses

The secondary endpoints for this study and a description of the analysis approach for each endpoint are provided below:

- Change in weekly mean worst pain from baseline to Week 12 and Week 4 as measured by the NRS will be analyzed using MMRM as outlined in Section 7.2.
- Proportion of patients achieving  $\geq 30\%$  and  $\geq 50\%$  improvement in mean NRS score from baseline to Week 4 and to Week 12 – will be summarized descriptively. Comparisons between the ricolinostat and placebo groups will be made using a Fisher's exact test.
- Change in mean BPI-SF pain interference score from Pre-Treatment/Day 1 to Week 12 will be analyzed using MMRM as outlined in Section 7.2.
- Change in mean BPI-SF pain interference score from Pre-Treatment/Day 1 to Week 4 will be analyzed using MMRM as outlined in Section 7.2.
- Change from baseline to Week 12 in the NTSS-6 will be analyzed using MMRM as outlined in Section 7.2.
- Change from baseline to Week 12 in Norfolk diabetic QOL-DN score will be analyzed using MMRM as outlined in Section 7.2.
- PGIC at Week 4 and Week 12 will be analyzed using an ANCOVA model with treatment group as a covariate.
- Rescue medication (acetaminophen) use will be analyzed based on mean daily used from baseline to Week 12 and mean weekly used from baseline to Week 12. Mean weekly use from baseline to Week 12 will be analyzed using the MMRM approach outlined for the primary efficacy analysis.

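### SAP Table 9 contradicts SAP 8.1 and 8.2 on whether UENS or pain is tested, and the SAP sends UENS to an NRS repeated-measures model that cannot be fitted to it as written

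*SAP*

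**What the plan says.** SAP 4.3.2, 8.1 and 8.2 agree that the second key secondary outcome is the change in UENS at 12 weeks. In the fixed sequence it follows the Week 12 and Week 4 pain tests.

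SAP Table 9 is titled for UENS, but its endpoint row reads "Change from baseline in weekly mean of daily average pain based on the UENS at Week 12". Its summary-measure row reads "Difference between ricolinostat arm and placebo arm as measured by change from baseline in average pain at Week 12", which is identical to the primary summary measure in SAP Table 1. Its population row requires baseline and post-baseline pain scores and no UENS score.

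Below Table 9 the SAP gives the method: "The analyses will follow those used for the primary efficacy analyses with a MMRM and multiple imputation as described in Section 7". The Section 7.2 model takes "weekly mean change from baseline in the NRS score at Weeks 1, 2, 4, 8 and 12 as the outcome". Its covariates are "baseline NRS score, visit, treatment group, concomitant medication for painful DPN (yes vs. no), treatment group by visit interaction term", plus baseline NRS by visit. Section 7.2 closes by extending this model to all analyses. The imputation code in SAP Tables 2 and 3 lists baseline NRS, concomitant medication and the twelve weekly NRS changes, and nothing for UENS. SAP 6.1.5.2 prescribes missing-at-random imputation for intermittent missing UENS and reference-based imputation for the rest.

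Protocol 10.3.4 planned an ANCOVA with "change from baseline in UENS at Week 12 as the outcome and baseline UENS score, treatment group" and concomitant DPN medication as covariates, and the synopsis says the same. SAP Section 1 states that the SAP prevails where the two differ on planned analyses.

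SAP 9 makes the same cross-reference for other outcomes, for example "Change from baseline to Week 12 in the NTSS-6 will be analyzed using MMRM as outlined in Section 7.2". BPI-SF and QOL-DN are treated alike. Protocol 10.3.5 had planned ANCOVA with each outcome's own baseline.

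**The concern.** UENS is the only alpha-controlled endpoint that addresses non-pain neuropathic signs, which is a stated key secondary objective. Its estimand table describes a variable that the trial does not collect: UENS is scored by physical examination and has neither daily pain ratings nor weekly means. The assigned model was written for a pain diary. An analyst working from the governing document would have to choose the outcome row to believe, the visits to keep, the baseline to adjust for and the variables to impute from. A confirmatory test should leave none of these open at unblinding. The protocol's workable plan cannot settle them, because the SAP overrides it.

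**Working it through.** **1. The plan's own figure.** The documents give no power or sample size for UENS. For the primary endpoint (difference 0.8, SD 2.35, two-sided 0.05, 80% power), n per arm = 2 × (1.960 + 0.842)² × (2.35/0.8)² ≈ 135.5, so 136 per arm or 272 in total. The t-test version gives 136.4, so 137 per arm and 274 in total, as stated. No sample-size figure is in dispute.

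**2. Which variable is tested.**

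| Place in SAP | Variable named |
|---|---|
| 2.2, 4.3.2, 8.1 lead-in, 8.2, title of Table 9 | UENS |
| Table 9, endpoint row | weekly mean of daily pain, attributed to UENS |
| Table 9, summary-measure row | average pain; UENS not named |
| Table 1, summary-measure row (primary) | same words as Table 9 |

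The table disagrees with its own title and with the sections that define the test.

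**3. Whether the model fits.** Section 7.2 needs outcomes at Weeks 1, 2, 4, 8 and 12. The schedule of assessments and the visit lists (Protocol 9.5.1 to 9.5.4 and 9.6.1) place UENS at Screening, Day 1 and Week 12, and then not until Week 24. Four of the five visits therefore have no UENS data. The visit terms, the interactions and the within-patient covariance matrix cannot be estimated. Once the empty visits are dropped, what remains is a one-visit linear model in treatment, concomitant medication and a baseline. The SAP names only baseline NRS for that last term.

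**4. Cost of omitting baseline UENS.** Assume equal variances σ² at baseline and Week 12, correlation ρ between them, and baseline NRS unrelated to UENS.
- Residual variance of the unadjusted change: 2σ²(1 − ρ).
- Residual variance in the ANCOVA with baseline UENS: σ²(1 − ρ²).
- Variance ratio: 2(1 − ρ)/(1 − ρ²) = 2/(1 + ρ). Standard-error ratio: √(2/(1 + ρ)).
- Power of a test that would have 80% under the ANCOVA: Φ(2.802/√(2/(1 + ρ)) − 1.960).

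| ρ (assumed) | Variance ratio | SE increase | Power, if 80% under ANCOVA |
|---|---|---|---|
| 0.4 | 1.43 | 20% | – |
| 0.5 | 1.33 | 15% | 68% |
| 0.7 | 1.18 | 8% | 73% |
| 0.8 | 1.11 | 5% | 76% |
| 0.9 | 1.05 | 3% | 78% |

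A dash means that power was not computed at that value.

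**5. Type I error.** In 4,000 simulated null trials with 137 per arm and ρ = 0.7, the rejection rate was 0.045 with baseline NRS as covariate and 0.050 with baseline UENS. The Monte Carlo standard error is √(0.05 × 0.95/4000) ≈ 0.003, so both are consistent with 0.05.

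**The case against.** The best defence is that the Table 9 wording is plainly carried over from the pain tables. Several other places name UENS, so no competent analyst would rerun the pain comparison in its place. The same analyst would drop the empty visits and use baseline UENS, which gives the protocol's ANCOVA. SAP 6.1.5.2 already has a rule for missing UENS, and SAP 5.1 provides for methods to be finalised during the blinded review. UENS is reached only after two pain tests succeed, in a Phase 2 proof-of-concept study. Both documents describe UENS as highly reproducible, so a high correlation, and hence a small loss, is plausible.

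Much of this stands. A reader might infer from Table 9 that the alpha-controlled test is not of UENS at all. The documents do not support that: SAP 8.2, which defines the sequence, names UENS, so this is an internal contradiction and not a redefinition. Nor does the SAP state that baseline NRS is the covariate for UENS. That is the literal result of the cross-reference, and the SAP is silent on any substitution. A reader might also suppose that a change score leaves chance baseline imbalance uncorrected. It does not: it subtracts baseline in full, which over-corrects when ρ < 1 and variances are equal, and under randomisation it stays unbiased.

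The defence fails on one point. It relies on the analyst departing from the text, and the text says that the Section 7.2 model serves all analyses. The rule in 6.1.5.2 is also incomplete. With a single double-blind post-baseline assessment, it is unclear which missing Week 12 value counts as intermittent, and no UENS imputation model is written.

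**Conclusion.** The point holds as a specification error in an alpha-controlled endpoint. Table 9 contradicts SAP 8.1 and 8.2 on the variable tested, and the governing analysis for UENS cannot be run as written. The primary analysis, the sample size of 274 and control of type I error are unaffected.

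The numerical cost is conditional. If UENS change is modelled without baseline UENS, the standard error rises by 3% to 20% for ρ from 0.9 down to 0.4. This rests on assumed ρ, equal variances and baseline NRS unrelated to UENS. If the analyst substitutes baseline UENS, no precision is lost, but the choice was not pre-specified.

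For BPI-SF, NTSS-6 and QOL-DN the same cross-reference leaves the baseline covariate unstated. These outcomes carry nominal p-values only, so less is at stake. It would go too far to call a repeated-measures model wrong for NTSS-6: Protocol 10.2.1.2.3 and SAP 4.2.4 describe weekly completion in the treatment period, while the schedule tables show only Week 12 after baseline in that period.

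**What to change.** Before unblinding, amend the SAP:

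1. In Table 9, restate the endpoint as change in UENS from baseline to Week 12, and the summary measure as the between-arm difference in the mean of that change.
2. In 8.1, name a single-time-point ANCOVA for UENS with baseline UENS, treatment and concomitant DPN medication (yes/no), in place of the reference to Section 7.
3. Write the UENS reference-based imputation using baseline and Week 12 UENS only, and say which missing Week 12 values, if any, are imputed as missing at random.
4. In Section 9, state that BPI-SF, NTSS-6 and QOL-DN each use their own baseline as covariate, with a single-time-point model for QOL-DN.
5. Reconcile the weekly and Week 12-only descriptions of NTSS-6 before choosing its model.

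The cost is SAP text and the matching program code. No design element, visit or sample size changes, and the blinded data review in SAP 5.1 is a natural occasion to do it.

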### 8.2. Adjustment for multiplicity

If the significance level for the primary endpoint is statistically significant then each of the key secondary endpoints will be tested using a fixed sequence method with the following testing sequence:

- Change in mean average pain intensity from baseline to Week 4 as measured by the NRS.
- Change in non-pain neuropathic signs after 12 weeks in patients as assessed by change in the UENS.

Nominal p-values will be reported for all other analyses.

## 9. Secondary analyses

The secondary endpoints for this study and a description of the analysis approach for each endpoint are provided below:

- Change in weekly mean worst pain from baseline to Week 12 and Week 4 as measured by the NRS will be analyzed using MMRM as outlined in Section 7.2.
- Proportion of patients achieving  $\geq 30\%$  and  $\geq 50\%$  improvement in mean NRS score from baseline to Week 4 and to Week 12 – will be summarized descriptively. Comparisons between the ricolinostat and placebo groups will be made using a Fisher's exact test.
- Change in mean BPI-SF pain interference score from Pre-Treatment/Day 1 to Week 12 will be analyzed using MMRM as outlined in Section 7.2.
- Change in mean BPI-SF pain interference score from Pre-Treatment/Day 1 to Week 4 will be analyzed using MMRM as outlined in Section 7.2.
- Change from baseline to Week 12 in the NTSS-6 will be analyzed using MMRM as outlined in Section 7.2.
- Change from baseline to Week 12 in Norfolk diabetic QOL-DN score will be analyzed using MMRM as outlined in Section 7.2.
- PGIC at Week 4 and Week 12 will be analyzed using an ANCOVA model with treatment group as a covariate.
- Rescue medication (acetaminophen) use will be analyzed based on mean daily used from baseline to Week 12 and mean weekly used from baseline to Week 12. Mean weekly use from baseline to Week 12 will be analyzed using the MMRM approach outlined for the primary efficacy analysis.

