#### **10.3.5 Secondary Outcome Measures**

The following secondary outcome measures will be analyzed as described for the primary efficacy analysis: change in mean BPI-SF pain interference score from Pre-Treatment/Day 1 to Week 4 and from Pre-Treatment/Day 1 to Week 12, change from baseline to Week 12 in the NTSS-6, and change from baseline to Week 12 in Norfolk Diabetic QOL-DN. ANCOVA models will be used for each of these analyses with the baseline value of the outcome, treatment group, and use of concomitant medication for painful DPN (yes vs. no) as covariates.

Proportion of patients achieving  $\geq 30\%$  and  $\geq 50\%$  improvement in mean NRS score from Pre-Treatment to the last week of treatment will be analyzed using a chi-square test. The PGIC at Week 4 and Week 12 will be analyzed using a two-sample t-test. Rescue medication (acetaminophen) use will be analyzed using a chi-square test.

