#### **3.2. Study population**

This study will enroll patients at up to 50 sites in the United States. Patients with Type 1 or Type 2 diabetes suffering from painful distal symmetric sensorimotor polyneuropathy (painful DPN) present for  $\geq 6$  months who meet all inclusion and exclusion criteria are eligible to participate. Eligible patients will be randomized in a 1:1 ratio to receive either ricolinostat or placebo.

Exhibit 1 and Exhibit 2 display the study's inclusion and exclusion criteria, respectively.

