### 6.1. Statistical methodology

#### 6.1.1. Sample size determination

The sample size for this study is planned to be approximately 274 evaluable patients. This sample size provides 80% power to detect a treatment difference of 0.8 points on the NRS. Assuming a pooled standard deviation of 2.35, this corresponds to a standardized effect size of approximately 0.34.

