#### 6.1.2. Analysis populations

The following populations are planned:

- Pre-randomized safety population (pSAF): All patients who have at least one observation during the pain observation period (day -14 to day -1/pre-treatment) and who were not randomized.
- Safety population (SAF): All patients who been randomized and received at least one dose of study drug
- Intent to treat (ITT) population: All patients randomized regardless of study drug administration
- Full analysis set (FAS) population: All patients who receive at least one dose of study drug, have a baseline average NRS score and, have at least one post-baseline average NRS score.
- Per-protocol population (PPP): All patients in the FAS population who have no major protocol violations, a valid baseline value of the NRS, meet all inclusion/exclusion criteria, missing no more than 2 weeks of diary data, and have a mean compliance rate of at least 60% (i.e., on average provide ratings on 4 or more days of each week).

6.1.3. *General considerations*

When presented, listings will be presented by patient number, treatment group, and measurement time.

In all analyses, the same number of decimal places as in the raw data will be presented for point estimates and univariate analysis. One more decimal place than in the raw data will be presented when reporting mean and standard deviation.

Continuous variables will be summarized by treatment group using descriptive statistics (n, mean, median, standard deviation, minimum, and maximum). For categorical variables, frequencies and percentages will be presented by treatment. The denominator for all categorical variables is the number of randomized patients.

All statistical testing will be based on a two-sided significance level of 0.05 unless otherwise stated.

*Baseline* is defined as the last observation prior to initiation of study medication.

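### The responder comparisons use an unadjusted Fisher's exact test and PGIC a treatment-only model; both are valid, but they give up a few points of power that two revised SAP sentences could recover

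*SAP*

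**What the plan says.** **Responders.** SAP section 9 summarises the proportions with at least 30% and at least 50% improvement in mean NRS at Weeks 4 and 12 descriptively and then adds: "Comparisons between the ricolinostat and placebo groups will be made using a" Fisher's exact test. No covariate, effect estimate or confidence interval is named. Protocol 10.3.5 has a different test: the same proportions "will be analyzed using a chi-square test". SAP section 1 makes the SAP govern where the two differ, so Fisher's test applies. No reason is given for the change.

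**PGIC.** SAP section 9: "PGIC at Week 4 and Week 12 will be analyzed using an ANCOVA model with treatment group as a covariate". Protocol 10.3.5 names a two-sample t-test.

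**Other secondary endpoints.** The primary model in SAP 7.2 includes baseline NRS and concomitant medication for painful DPN (yes/no). SAP section 9 carries that model over to worst pain, BPI-SF interference, NTSS-6 and QOL-DN, and uses the primary MMRM approach for weekly rescue use.

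**Status.** Both endpoints lie outside the fixed sequence in SAP 8.2 and receive nominal p-values. SAP 6.1.5.3 analyses them as complete cases.

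**The concern.** Three features stand out. First, the SAP moves from a test whose size is close to nominal to one that is conservative at this sample size. Second, an ANCOVA with no covariate is a t-test under another name, so the SAP wording suggests an adjustment that is not made. Third, two baseline variables are modelled for most of the neighbouring endpoints but not for these two, with no explanation. Randomisation is blocked by site only (Protocol 7.4.2), so neither variable is balanced by design.

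What is at stake is precision. Protocol 7.2 says the study is meant to inform later designs, and a responder difference with a confidence interval is a natural input for that. The SAP provides only a test.

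**Working it through.** **Inputs from the documents.** Significance level (SAP 6.1.3): "All statistical testing will be based on a two-sided significance level of 0.05 unless otherwise stated". From SAP 6.1.1: 274 evaluable patients in total, target power 80%, target difference 0.8 NRS points, SD 2.35, effect size 0.34. Allocation is 1:1 (SAP 3.2), hence 137 per arm.

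**Inputs assumed.** Responder rates, and the correlation of PGIC with the covariates. The documents state neither. All 137 per arm are taken as observed, which is an upper limit under complete-case analysis.

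**1. The plan's own figure.** n per arm = 2(1.960 + 0.842)² × (2.35/0.8)² = 135.5, so 136 per arm and 272 in total, against 274 stated. At 137 per arm the power is 80.4% (80.2% with the noncentral t). The stated figure reproduces. The plan states no power for responders or PGIC.

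**2. Fisher against chi-square.** All 138 × 138 outcomes of two binomials with n = 137 were enumerated. Fisher's two-sided p sums the hypergeometric probabilities no larger than the one observed. The chi-square is Pearson's, uncorrected: |p₁ − p₂| / √(2p̄(1 − p̄)/137) compared with 1.96.

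True size over common rates of 15-55%: Fisher 3.4-3.9%, chi-square 4.6-5.2%.

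| Assumed rates, placebo vs ricolinostat | Fisher power | Chi-square power | Gap (points) |
|---|---|---|---|
| 40% vs 57% | 76.2% | 79.8% | 3.6 |
| 30% vs 46% | 75.1% | 78.9% | 3.7 |
| 20% vs 34% | 70.3% | 74.7% | 4.4 |
| 40% vs 55% | 64.8% | 69.2% | 4.4 |
| 20% vs 33% | 63.9% | 68.7% | 4.8 |
| 15% vs 28% | 70.4% | 75.5% | 5.1 |

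Gaps are taken before rounding. The first three rows imply a shift of about 0.43 SD on a probit scale, more than the design effect of 0.34. With a shift of 0.34 from placebo rates of 40%, 30% and 20%, Fisher and chi-square give 55.0% and 59.7%, 54.6% and 59.5%, and 48.5% and 53.8%. Power is lower, but the gap remains at 4.7-5.3 points.

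**3. Further gain for responders from covariates.** This was simulated with 2,000 trials per scenario. Assumptions: baseline NRS mean 6.5, SD 1.3; change SD 2.35; treatment effect 0.8; half the patients on DPN medication; placebo improvement 1.2 or 1.8; baseline-change correlation from −0.5 to +0.3. Adjusted logistic regression (likelihood-ratio test) was compared with chi-square:

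- Smallest gain: 55.9% to 56.5%, or 0.6 points (50% responders, placebo improvement 1.2, correlation −0.3, no medication effect).
- Largest gain: 54.7% to 63.6%, or 8.9 points (30% responders, placebo improvement 1.8, correlation +0.3, medication effect 0.8).

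Response is defined as a percentage of baseline, so baseline pain is already partly used. That is why the gain can be as low as about 1 point.

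**4. PGIC.** If the covariates have correlation r with PGIC, the residual SD is multiplied by √(1 − r²). Suppose unadjusted power is 80.3% (effect 0.34, 137 per arm):

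- r = 0: 80.3%.
- r = 0.2: variance down 4%, standard error down 2.0%, power 81.9% (+1.6 points).
- r = 0.3: variance down 9%, standard error down 4.6%, power 83.9% (+3.6 points).

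**The case against.** The case for leaving the SAP alone is reasonable. Fisher's test is a valid exact test, the SAP is entitled to supersede the protocol, and chi-square can slightly exceed 5% (up to 5.2% here). The responder result is first of all a descriptive summary, and the p-values are nominal, so no confirmatory claim turns on crossing 0.05. PGIC has no baseline value of its own, and background medication is not a stratification factor that the analysis must include. All of this stands, and it sets the weight of the point.

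A reader might infer more than the documents support:

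- *That the responder p-values are wrong.* They are not. They are conservative relative to a test with size near 5%.
- *That the power loss shown comes from omitting covariates.* It does not. The 4-5 points compare two unadjusted tests, and restoring the protocol's chi-square would recover them. The covariate gain is separate and rests on prognostic strength that the documents do not give.
- *That adjustment has no downside.* It needs a stated variance method and a rule for sparse cells or non-convergence.

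Nominal status does not make precision irrelevant, though, and nothing in the SAP explains why these two endpoints are treated differently from the others in the same list.

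**Conclusion.** The point holds as a minor, cheap improvement. The firm part is that Fisher's test runs at about 3.4-3.9% true size with 137 per arm and costs about 4-5 points of power against the protocol's chi-square. The size of that loss depends on assumed responder rates, but it appeared in every scenario tried. The less certain part is the covariate gain: possibly only about 1 point for responders, and for PGIC about 2-4 points at an assumed correlation of 0.2-0.3 and none at zero. As worded, the PGIC ANCOVA is a t-test. The primary and key secondary conclusions are not affected.

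**What to change.** Revise two sentences in SAP section 9 before unblinding; the blinded data review in SAP 5.1 already allows methods to be finalised then.

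- **Responders:** logistic regression with treatment, baseline NRS and DPN medication (yes/no). Report the standardised risk difference, which is the average over all analysed patients of the predicted response probability under ricolinostat minus that under placebo, with a 95% CI by the delta method or bootstrap (name one). Keep the protocol's unadjusted chi-square as the supportive analysis and as the fallback if the model does not converge.
- **PGIC:** ANCOVA with treatment, baseline NRS and DPN medication. First reconcile the scale: Protocol 10.2.1.2.2 makes 7 the best outcome and SAP 4.2.3 makes 7 the worst, so the sign of any PGIC effect is ambiguous until the anchors are checked against the form actually administered.

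No new data are needed. The cost is a little more programming and a stated variance and fallback rule.
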